## **Research Plan**

- **Study Design**

- Randomized Controlled Trial

- **Setting for the study**

- Patients of Cincinnati Urogynecology Associates and/or Tri-State Gynecology Oncology, TriHealth, Inc. undergoing total vaginal, laparoscopic assisted, total laparoscopic, or robotic hysterectomy at Good Samaritan Hospital or Bethesda North Hospital will be eligible for enrollment.
- The study will be offered to those patients found to meet all inclusion criteria and none of the exclusion criteria via phone (see attached script), in office or prior to surgery in the preoperative holding area
- Patient will sign Informed Consent and Authorization prior to surgery, but not to exceed 6 months before surgery.
- Following enrollment, a SNOSE (Sequentially-Numbered, Opaque, Sealed Envelopes) will reveal group allocation.
  - Intervention group:
    - Patients randomized to the chlorhexidine group will undergo presurgical vaginal aseptic preparation using 4% chlorhexidine solution.
    - Vaginal culture swabs will be collected following induction of general anesthetic, prior to their vaginal preparation.
    - Swabs will be collected subsequently at times marked 30 minutes, 60 minutes and 90 minutes following preparation allowing for +/- 5 minutes.
    - EPIC will be interrogated, looking at the time period from day of surgery to 30 days post operatively, for evidence of surgical site infections, including superficial incisional, deep incisional and organ space infections. Incidents of surgical site infection will be determined by CDC guidelines. (see Appendix A)

- Control group:
  - Those patients randomized to the povidone-iodine group will have their presurgical vaginal aseptic preparation performed using 10% povidone-iodine solution.
  - They will have culture swabs collected following induction of general anesthetic, prior to their vaginal preparation.
  - Swabs will be collected subsequently at times marked 30 minutes, 60 minutes and 90 minutes from preparation allowing for +/- 5 minutes.
  - EPIC will be interrogated, looking at the time period from day of surgery to 30 days post operatively for evidence of surgical site infections, including superficial incisional, deep incisional and organ space infections. Incidents of true surgical site infection will be determined by CDC guidelines. (**Appendix A**)
- **Participants**
  - Study population: All women 18 years of age or older, who plan to undergo total vaginal, laparoscopically assisted vaginal, total laparoscopic, or robotic-assisted laparoscopic hysterectomy, with or without additional concomitant procedures by a physician at Cincinnati Urogynecology Associates or Tri-State Gynecology Oncology, TriHealth Inc. and will be approached for recruitment in their office or in the pre-operative holding area.
  - Inclusion/Exclusion criteria:
    - Inclusion
      - Adults 18 years of age and older
      - English speaking
      - Undergoing total vaginal, laparoscopic assisted vaginal, total laparoscopic, or robotic-assisted laparoscopic hysterectomy by a physician at Cincinnati Urogynecology Associates or Tri-State Gynecology Oncology TriHealth Inc.

- Concomitant procedures such as vaginal vault suspension, suburethral sling, cystoscopy, enterocele repair, anterior or posterior colporrhaphy, bilateral salpingectomy or salpingoophorectomy, staging procedures, lymph node sampling and other indicated procedures will be included
- Ability to provide consent
- Exclusion
  - Unwillingness to participate in the study
  - Non English speaking
  - Patients that do not undergo a hysterectomy
  - Reported allergy to iodine or chlorhexidine preparation solutions
  - Patients undergoing planned debulking surgery for ovarian, fallopian tube or primary peritoneal cancers
  - Current infection necessitating hysterectomy
  - Active sepsis, pelvic abscess or pelvic inflammatory disease
  - Patient receiving Flagyl for treatment of vaginitis or for surgical prophylaxis during the perioperative period, including day of surgery.
- Sample Size
  - Given the incidence of infection following hysterectomy, a surrogate outcome was felt to be necessary in order to complete the study in a timely fashion. Therefore, using the only published randomized controlled trial, we selected contamination of the field as our outcome measure.
  - Contamination is defined as having >5000 bacteria within a culture.
  - The previous study suggested a 22% difference in bacteria contamination, therefore our sample size was calculated to be 71 patients per arm to

detect a 22% difference in cultures defined as contaminated at 90 minutes from surgical preparation.

- *Power Analysis*
  - Our calculation demonstrated need to enroll 60 patients in each arm based on the following:
    - A difference of 22% in number of cultures found to have >5,000 bacteria growing 90 minutes from preparation
    - Significance at 0.05
    - Power at 80%
    - Odds ratio was 0.289
    - Assuming an estimated loss rate of 15%, the number of patient enrollment per arm was set to 71, for a total of 142 patients. [Attrition calculation: (60/0.85)]
      - Subjects will be randomized by using a random numbers table and sealed sequential envelopes prepared by an independent statistician. Patients of Cincinnati Urogynecology Associates and Tri-State Gynecology Oncology will have independent randomization schedules.
- **Data Collection**
  - *Primary outcome:*
    - The percent of samples considered contaminated at 90 minutes from preparation between groups.
  - *Secondary Outcomes:*
    - The percent of samples considered contaminated at 30 and 60 minutes from preparation between groups.
    - Number of samples reaching a bacterial load of 100,000 following vaginal preparation at any of the specified time points.
    - The change in bacterial count over time. Specific attention will be given to investigate the following bacteria, most commonly identified in association with postoperative infections:

- *Streptococcus Agalactiae*
- *Staphylococcus aureus*
- *Escherichia Coli*
- *Gardnerella Vaginalis*
- *Enterococcus Faecalis*
- *Bacteroides Fragilis*
- Also included, specific bacteria associated with the condition of bacterial vaginosis:
  - *Gardnerella*
  - *Mobiluncus species*
  - *Prevotella*
  - *Bacteroides*
  - *Peptostreptococcus*
- The number of postoperative infections in each group
- *General Demographic Data*
  - Age, BMI, race, past medical history, home medications, allergies , smoking history, prolapse stage, cancer stage, procedures performed, length of stay, surgical and postoperative complications, and estimated blood loss
- *Data Collection tool*
  - A data collection tool will be utilized
- Please see **Appendix B** for evidence regarding outcome measures
- **Intervention or experimental aspect of the study**
  - *Vaginal preparation*
    - The vaginal scrub will be performed by the OR team according to standard procedures for asepsis within the TriHealth System
    - Solutions:
      - 4% chlorhexidine

- 10% povidone-iodine
- *Sample Collection*
  - Samples will be collected in a standard fashion in the operating room after the patient has been anesthetized
    - The ESwab liquid amies collection and transport system will be utilized.
    - The swab will be thoroughly rubbed along the vaginal surface in a circumferential pattern, careful to sample the entire surface of the vagina, beginning at the fornix and traveling towards the introitus for 10 seconds. The sample will avoid the cervical os or peritoneum.
    - A sample will be collected prior to any vaginal preparation, at 30 minutes, 60 minutes and 90 minutes from preparation (This last sample may be collected at end of surgery if prior to 90 minutes)
    - The samples will be labeled with the participant's study ID, name, and time of collection, annotated as time 0, 30, 60, or 90.
    - The samples may be collected +/- 5 minutes around the determined time to allow for surgical flow and circumstantial adjustment.
    - Swabs will then be sent to the laboratory for analysis
    - An in-service will be provided to teach all participating physicians the standard method of collecting swabs as described above.
  - *Laboratory Procedure Outline*
    - Samples will be handled by a single technician within the laboratory. This technician will be paid through study funds while they perform these duties.
    - The laboratory personnel will be blinded to the participants group assignment

- Sterile calibrated loops will be used to inoculate the specimen onto specific agar for cultures:
  - *Blood Agar*
  - *MacKonkey Agar*
  - *CAN Agar*
  - *Anaerobic Agars*
    - *Brucella*
    - *BBE/KUL*
    - *PEA*
- The inoculate will be streaked according to techniques commonly utilized in urine culture to facilitate analysis

○ TriHealth Laboratory\MIC\OAK\Procedures\Active\Cultures\Bacteriology\Urine Cultures.doc

- The cultures will be read approximately 48-72hrs from inoculation
- A colony count will be performed on each sample
- Individual strains will be isolated and identified
- The individual pathogens will be identified using the MALDI (Matrix Assisted Laser Desorption/Ionization-Time of Flight) test, by Bruker Daltonics.
  - An affordable & reliable bacterial identification method. Based on mass spectrometry, using qualitative in vitro diagnostics, ribosomal proteins are analyzed and compared to two proprietary libraries for a match and identity verification.
  - Capable of identifying more than 200 organisms
  - <http://www.midilabs.com/maldi-tof>
- Bacterial Vaginosis will be identified through a modified Nugent method.

- Utilizing colony counts obtained from culture plate reading and correlating this with specific identities found in the MALDI test, a Nugent score will be reported.
- Nugent Score
  - Points will be awarded based on three morphotypes:
    - Medium to large gram positive rods
    - Small gram negative or variable rods
    - Curved gram negative or variable rods
  - Each of these morphotypes will be assigned a score based on their initial count:
    - 0 = No morphotypes
    - 1 = Less than 1,000
    - 2 = 1,000 – 4,000
    - 3 = 5,000 – 30,000
    - 4 = >30,000
  - The score for the three morphotypes is then added, and any score >7 is consistent bacterial vaginosis, and a score <3 is normal flora.
  - Scores will be generated for each specific time point to allow trending following vaginal preparation.
- *Safety Considerations*
  - Povidone-iodine is FDA approved for use as a vaginal scrub solution and is considered to be safe.
  - Though this application would represent an off-label use, 4% chlorhexidine is considered a safe alternative to povidone-iodine for use as a surgical scrub of the vagina by the American College

of Obstetricians and Gynecologists. TriHealth also includes chlorhexidine as a part of the standard surgical bundle.

**(Appendix C)**

- **Statistical Analysis**

The primary outcome is the proportion of contamination (defined as having >5000 bacteria within a culture) at 90 minutes from initial preparation. Logistic regression will be implemented to compare the odds ratio between two groups. Furthermore, multiple logistic regression will be utilized to test for confounding variables. For continuous variable, descriptive statistics will be reported with mean and standard deviation (or median and interquartile range). Difference between two groups will be evaluated in each time point by independent Student's t-test or nonparametric equivalent (Mann Whitney-U test). Alpha < 0.05 will be considered statistically significant.

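### The primary logistic regression leaves out the pre-preparation bacterial count and the practice; adjusting for both costs almost nothing and may gain power, though the gain could be nil

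*Combined protocol and SAP*

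**What the plan says.** The Statistical Analysis section defines the primary outcome as the proportion of cultures above 5,000 bacteria at 90 minutes. It then says: "Logistic regression will be implemented to compare the odds ratio between two groups". No covariate appears in that sentence. The next one adds: "Furthermore, multiple logistic regression will be utilized to test for confounding variables". It does not list the variables or say whether that model or the two-group model decides the trial. The natural reading is that it supplements the first.

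Two candidate covariates are already in the design.

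- **Time-0 count.** Under Research Plan, the chlorhexidine arm is sampled before treatment: "Vaginal culture swabs will be collected following induction of general anesthetic, prior to their vaginal preparation". The povidone-iodine arm is treated alike: "They will have culture swabs collected following induction of general anesthetic, prior to their vaginal preparation". The Laboratory Procedure Outline adds "A colony count will be performed on each sample" and "The laboratory personnel will be blinded to the participants group assignment".
- **Practice.** Under Power Analysis, the two participating practices "will have independent randomization schedules". The method is given as "Subjects will be randomized by using a random numbers table", with sealed envelopes and no mention of blocking.

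**The concern.** The time-0 count comes from the same swab and culture procedure as the outcome, and it precedes the antiseptic, so treatment cannot have affected it. If women with a heavier starting load are more often contaminated at 90 minutes, leaving the count out of the model gives up power the trial has already paid for. Practice is known at entry and defines the randomisation schedules, so it too can be adjusted for at no cost in data.

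A second issue follows from having two logistic models. Adjusted and unadjusted tests do not always agree, and with no stated deciding model or covariate list the choice could be made after the results are known.

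**Working it through.** **1. Reproduce the plan's sample size.** Power Analysis gives a 22-point difference, an odds ratio of 0.289, significance 0.05, power 80%, 60 per arm and 15% loss. The arm rates are not printed. Rates of 36% and 14% satisfy both effect figures: (0.14/0.86)/(0.36/0.64) = 0.289. The mirror pair 86% and 64% does so too.

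Two-sided pooled test, mean rate 0.25:

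n = [1.960·√(2·0.25·0.75) + 0.842·√(0.36·0.64 + 0.14·0.86)]² / 0.22² = [1.960·0.6124 + 0.842·0.5923]² / 0.0484 = 59.6, so 60 per arm.

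60/0.85 = 70.6, so 71. Both planned figures reproduce with no allowance for covariates. The same formula gives power of 80.3% at 60 per arm, 81.6% at 62 and 86.0% at 70.

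**2. Room for covariates.** Expected contaminated samples are 60·0.36 + 60·0.14 = 21.6 + 8.4 = 30. Arm, practice and count make three coefficients, or 10 events each.

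**3. Simulated power.** Settings: 120 patients, half in each practice (assumed), marginal rates held at 36% and 14%, Wald tests, simple allocation within practice, 8,000 trials (standard error about 0.45 points). Strengths are assumed log-odds for practice, then per SD of log count.

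| Practice, count | Unadjusted | + practice | + count | + both |
|---|---|---|---|---|
| 0, 0 | 80.6% | 80.5% | 80.4% | 80.4% |
| 0.5, 0.5 | 79.6% | 79.7% | 81.0% | 81.4% |
| 1, 1 | 79.5% | 80.6% | 84.5% | 85.6% |
| 1, 1.5 | 80.5% | 81.4% | 89.8% | 90.8% |

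The count supplies most of the gain; practice alone adds about 1 point or less. With balance forced within practice, the model with both covariates gives 80.1, 83.8, 86.6 and 90.9%, against 80.1, 82.0, 80.7 and 80.3% unadjusted.

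**4. Missing and capped counts.** The secondary outcomes include samples reaching 100,000, so any upper counting limit is at or above that level, which is 20 times the 5,000 threshold. The share of time-0 counts at such a limit is not given. With 5% of time-0 counts missing and set to the mean (simple allocation, 10,000 trials), unadjusted / both:

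| Practice, count | No limit | 50% at limit | 80% at limit |
|---|---|---|---|
| 0, 0 | 80.1 / 79.6% | 79.9 / 79.6% | 79.8 / 79.1% |
| 0.5, 0.5 | 80.4 / 81.6% | 80.2 / 81.4% | 80.0 / 80.2% |
| 1, 1 | 79.7 / 86.1% | 79.2 / 83.7% | 80.1 / 82.0% |
| 1, 1.5 | 79.6 / 89.2% | 80.3 / 85.6% | 80.4 / 82.5% |

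With no limit, the second and third rows correspond to about 62 and 70 per arm in step 1: a gain of roughly 2 to 10 patients per arm.

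**5. Validity.** With 25% in both arms, rejection was 4.5–4.8% unadjusted and 4.8–4.9% adjusted. Coverage of the 95% interval for the conditional odds ratio was 95.0–95.8%. The arm coefficient could not be estimated in at most 4 of 10,000 trials in any setting of step 4.

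**6. Sensitivity, both covariates, three prognostic settings.** Mirror rates: 81.9, 87.1, 90.0%. Practices split 75/25: 81.7, 85.9, 89.7%. True count effect a step at the median: 80.7, 84.1, 86.2% (unadjusted 79.2, 80.1, 79.9%).

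**The case against.** The plan already intends an adjusted model, so adjustment is not absent; reading that model as supplementary is an inference. The point stands in narrower form: its covariates and its role are not fixed.

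No figure in the documents links the time-0 load to contamination 90 minutes after antisepsis. The larger gains need odds ratios of about 2.7 or 4.5 per SD of log count (log-odds 1.0 and 1.5); at log-odds 0.5 the gain is only 1.2 to 1.8 points. An unprepared vagina is also the sample most likely to reach a counting limit, given loop-inoculated plates streaked by urine-culture technique. Both objections stand, and they are why the gain may be nil.

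The adjusted odds ratio is conditional. For the same 36% and 14% it is 0.271, 0.225 and 0.182 in the three prognostic settings, so it cannot be set directly against the planning value of 0.289. The hypothesis is worded as a percentage of contaminated samples, which a conditional odds ratio does not express. This is a real cost to interpretation. However, the plan's own analysis already targets an odds ratio, and the risk difference would still be reported.

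Finally, practice is a weak addition by itself. With a random numbers table and no stated blocking, the separate schedules do not guarantee balance within practice and give little reason on their own to adjust.

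**Conclusion.** The point holds as an efficiency improvement to a valid analysis. Adjustment changes power by between a loss of 0.7 points (neither covariate prognostic, 80% of counts at a limit) and a gain of about 10 points (strong prognostic effect, no limit). For weak to moderate effects and no limit the gain is about 1 to 6 points. These figures rest on the inferred 36% and 14%, 120 evaluable patients, and covariate strengths and limit shares that the documents do not supply.

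The need to name the deciding model is firmer than the size of the gain: adjusted and unadjusted tests reached different verdicts in 2.5–12.3% of simulated trials.

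**What to change.** Specify one primary analysis: logistic regression of 90-minute contamination on arm, practice and log10(time-0 count + 1).

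- Set counts at the laboratory's upper limit to that limit.
- Replace a missing time-0 count by the mean of the observed log10 values across both arms, so that no patient is dropped for it.
- Base the primary conclusion on the arm coefficient of this model alone: odds ratio, confidence interval and p-value.
- Report the unadjusted odds ratio and the risk difference as supportive.
- Record before unblinding that the adjusted model stands if they differ, and that its odds ratio is conditional.
- Add no further covariates to this model, given about 30 expected events.

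The cost is small: no new samples and no change to the sample size. The laboratory must state its upper counting limit. The price is the conditional interpretation of the odds ratio and, if neither covariate matters, up to 0.7 points of power.

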### Hypothesis or Research Question

- We hypothesize that the percent of samples considered contaminated by bacterial count at 90 minutes from preparation will be 20% lower in the group that receives chlorhexidine preparation vs povidone-iodine.

- We further hypothesize that this trend will be demonstrated throughout the 30-90 minute time window following vaginal preparation.
- Additionally, we hypothesize chlorhexidine will reduce bacterial counts of pathogens more commonly associated with post operative gynecologic infections better than povidone-iodine.
- Finally, we hypothesize chlorhexidine will clear the pathogens associated with bacterial vaginosis more effectively than povidone-iodine.

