Therefore, the purpose of our study is to use a randomized controlled trial to determine whether chlorhexidine is superior to povidone-iodine as an aseptic solution in the vagina by comparing its effects on bacterial count, change in common pathogens responsible for postoperative infection and colony counts throughout the time course of a hysterectomy.

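### The secondary outcome of change in bacterial count over time is analysed only by separate two-sample tests at each time point, which use neither the time-0 count nor practice and do not estimate whether the arm difference changes

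*Combined protocol and SAP*

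**What the plan says.** Under Data Collection, the secondary outcomes include "The change in bacterial count over time", with named organisms of special interest. No formula, scale or reference time is given for change. The closing paragraph of the Background makes "colony counts throughout the time course of a hysterectomy" part of the study's purpose.

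The Sample Collection section supplies the data: "A sample will be collected prior to any vaginal preparation" and again at 30, 60 and 90 minutes, with samples "annotated as time 0, 30, 60, or 90". Under Power Analysis, the two recruiting practices "will have independent randomization schedules".

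In the Statistical Analysis section, continuous variables receive descriptive summaries (mean and SD, or median and interquartile range) and then: "Difference between two groups will be evaluated in each time point by independent" Student's t-test or the Mann-Whitney U test, at a 0.05 threshold. The only regression is logistic. It follows the sentence on the binary primary outcome, and its multiple version names no covariates. No repeated-measures model, baseline-adjusted count analysis or arm-by-time term appears anywhere.

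**The concern.** The listed outcome is about change and time. The planned tests look at one time at a time, and three things are lost.

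- **Baseline information.** The time-0 swab is collected from every patient, but it does not enter the comparison of later counts as a covariate. If earlier and later counts are correlated, precision is given away.
- **The time course.** No quantity in the plan measures whether the arm difference at 90 minutes differs from that at 30. A reader would have to compare which tests reach 0.05, and that pattern varies by chance even when the true difference is constant.
- **The meaning of change.** An analyst could later take it as the count minus its time-0 value. That reading can be less precise than the count itself.

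At stake are the precision and interpretation of one secondary outcome.

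**Working it through.** **The plan's own figure.** The only size calculation is for the binary primary outcome. The arm rates are not stated, but a difference of 0.22 with odds ratio 0.289 implies 36.0% and 14.0% (or the mirror pair, 86.0% and 64.0%). The pooled two-sided formula at 0.05 and 80% power gives 59.6, so 60 per arm; 60/0.85 = 70.6, so 71. The plan's figures reproduce. They say nothing about counts, so everything below is illustrative.

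**Inputs.** n = 60 evaluable per arm, alpha 0.05 and power 80% are from Power Analysis. Two-sided testing is assumed. The documents give no SD or within-patient correlation for counts, so these are also assumed: r0 = correlation of the time-0 count with a later count; r1 = correlation between the 30- and 90-minute counts. Effects are in SDs of the post-preparation count. k = 1.960 + 0.842 = 2.802.

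**Detectable arm difference at one time.**

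- Planned test: k·sqrt(2/60) = 2.802 × 0.1826 = 0.511 SD.
- Time-0 count as covariate: k·sqrt(2(1 − r0²)/60).
- Change from time 0, equal SDs before and after preparation: k·sqrt(4(1 − r0)/60).

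| r0 | Planned test | Time-0 covariate | Change from time 0 |
|---|---|---|---|
| 0 | 0.511 | 0.511 | 0.723 |
| 0.3 | 0.511 | 0.488 | 0.605 |
| 0.5 | 0.511 | 0.443 | 0.511 |
| 0.7 | 0.511 | 0.365 | 0.396 |

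The covariate analysis multiplies the variance by 1 − r0²: 0.91, 0.75 and 0.51 at r0 = 0.3, 0.5 and 0.7. The change score is worse than the raw count when r0 is below SD0/(2·SDpost), where SD0 and SDpost are the SDs at time 0 and after preparation. This is 0.5 only if the two SDs are equal.

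**Chance disagreement between the 30- and 90-minute tests.** Take the same true arm difference at both times. At 60 per arm, a difference of 0.40 SD gives 0.40/0.1826 = 2.19, so power is Φ(2.19 − 1.96) = 59% per test. The chance that exactly one test is significant is 2 × [power − P(both significant)], from the bivariate normal with correlation r1.

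| Power per test | r1 = 0.3 | r1 = 0.5 | r1 = 0.7 |
|---|---|---|---|
| 60% | 0.388 | 0.322 | 0.245 |
| 80% | 0.268 | 0.226 | 0.174 |

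**What the 30-to-90 contrast can detect.** k·sqrt(4(1 − r1)/60) = 0.605, 0.511 and 0.396 SD at r1 = 0.3, 0.5 and 0.7.

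**Nominal or actual minutes.** The last swab may be early: "This last sample may be collected at end of surgery if prior to 90 minutes". A simulation assumed r0 = 0.3, r1 = 0.5 and an arm difference falling linearly by 0.60 SD from 30 to 90 minutes.

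- With 30% of last swabs early (62-85 minutes) but analysed as 90, the estimated fall is 0.55 SD; with 50% early (62-80 minutes) it is 0.51 SD.
- Modelling actual minutes recovers 0.60 SD. The standard error at 90 minutes then becomes 0.192 or 0.213 SD, against 0.183 SD for the planned unadjusted test: 0.192/0.183 = 1.05 and 0.213/0.183 = 1.17.

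Actual-minute modelling therefore removes a modest bias and, at this r0, costs more precision than the time-0 covariate gains.

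**The case against.** The strongest reply is that the planned tests are valid and largely answer what is asked. The hypothesis that "this trend will be demonstrated throughout the 30-90 minute time window" concerns contamination, and separate comparisons at each time address it. No hypothesis predicts a changing arm difference, and the plan also commits to descriptive summaries, so readers would see more than p-values. This stands against any suggestion that the tests are wrong. It does not supply an analysis of the listed outcome.

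Other points on that side:

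- **Change from time 0.** A reader might infer that the plan will test raw change. It does not say so. The change-score figures show what an undefined term could cost, not what the plan costs.
- **Time 0.** Each time point may include time 0, but that would only compare the arms at baseline. It would not adjust later comparisons.
- **Logistic regression.** Its unnamed confounders could include baseline count or practice, but that model is for a binary outcome.
- **Practice.** A random numbers table is described and no blocking is mentioned. Separate unblocked lists do not force balance, so omitting practice does not miscalibrate the tests. This part of the case is weak and has no magnitude attached.
- **Sampling time.** A reader might infer that only nominal times are kept. The Sample Collection section says labels also carry the time of collection, and the data collection tool is not shown.
- **Primary outcome.** A reader might conclude that the early-swab allowance matters only for this secondary outcome. It governs the swab that defines the primary 90-minute outcome too, and should be taken up as a separate point.

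**Conclusion.** The point holds as a minor one. The plan collects a baseline count and repeated later counts, lists change over time as an outcome, and analyses it only cross-sectionally. That rests on the text alone.

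The benefit depends on correlations that the documents do not give. The detectable difference falls from 0.51 to 0.49, 0.44 or 0.37 SD at r0 = 0.3, 0.5 or 0.7, so the gain is small at 0.3 and absent at 0. Chance disagreement between the 30- and 90-minute tests is about 25-39% at 60% power per test and 17-27% at 80%, for r1 from 0.7 down to 0.3.

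Two stronger readings are not supported. The planned tests are not invalid for the arm difference at each post-preparation time. Nor would an arm-by-time test prove a stable effect: it detects only about 0.40-0.61 SD, so a non-significant result does not show stability. The lack of a count model does not touch the primary logistic analysis or the sample size.

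**What to change.** In the Statistical Analysis section, define the outcome as log10(count+1) at 30, 60 and 90 minutes (nominal times). Analyse it in one repeated-measures model with arm, time, arm-by-time, time-0 log10 count and practice, with robust standard errors. Report:

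- the baseline-adjusted arm difference with a 95% confidence interval at each time;
- the 30-to-90 contrast of the arm difference with its 95% confidence interval, stating that a wide interval or non-significant result is not evidence of a constant effect.

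Do not use raw change from time 0 as the tested variable. Keep the Mann-Whitney tests as a sensitivity analysis because of zero counts. Modelling actual sampling minutes is at most a further sensitivity analysis, because it can widen the 90-minute standard error.

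**Cost.** Some SAP wording and a little programming; no extra patients or swabs. The log transform handles zeros imperfectly. If time-0 counts are unrelated to later counts, the standard error is about 1% larger.

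### The pathogen and bacterial vaginosis hypotheses have no success criterion and no error control: every test is judged at 0.05, at each time point, over 6 and 5 listed organisms

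*Combined protocol and SAP*

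**What the plan says.** The Statistical Analysis section names contamination at 90 minutes as the primary outcome, analysed by logistic regression. For continuous variables it compares the two groups at each time point by t-test or Mann-Whitney test. It closes with the only decision rule in the plan: "Alpha < 0.05 will be considered statistically significant". It contains no adjustment, no testing order, no single model over time, and no statement that secondary analyses are exploratory.

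The Hypothesis section adds three secondary hypotheses, all favouring chlorhexidine. One extends the contamination result to the 30 to 90 minute window. Another reads: "we hypothesize chlorhexidine will reduce bacterial counts of pathogens more commonly associated with post operative gynecologic infections better than povidone-iodine". The last concerns clearance of organisms linked to bacterial vaginosis.

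Under Data Collection, Secondary Outcomes, the change in bacterial count over time is introduced with "Specific attention will be given to investigate the following bacteria, most commonly identified in association with postoperative infections", followed by six organisms. Five more are listed for bacterial vaginosis. Gardnerella and Bacteroides appear on both lists, as species on the first and by genus on the second.

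The Power Analysis concerns the primary comparison only.

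**The concern.** The pathogen hypotheses are worded as efficacy claims, and the plan foresees presentation and publication. Each has its own organism list, but nothing says which organism, which time, or how many positive tests would count as confirmation. Under the rule as written, one organism at one time with p < 0.05 could be reported as showing that chlorhexidine acts better on the pathogens that cause infection. A chance difference in Gardnerella or Bacteroides could be used for both hypotheses. With this many opportunities, a nominally significant pathogen result would say little about whether the products differ.

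**Working it through.** **1. The plan's own figure: the primary test.** Inputs from the Power Analysis: "A difference of 22% in number of cultures found to have >5,000 bacteria growing 90 minutes from preparation", "Significance at 0.05", 80% power and "Odds ratio was 0.289". The rates that give both the difference and the odds ratio are about 36% and 14% (or the mirror pair, 86% and 64%):

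- (0.14/0.86) / (0.36/0.64) = 0.163/0.5625 = 0.289.
- Mean rate 0.25. Two-sided 0.05, no continuity correction: n = [1.96 × √(2 × 0.25 × 0.75) + 0.842 × √(0.36 × 0.64 + 0.14 × 0.86)]² / 0.22² = (1.200 + 0.499)² / 0.0484 = 59.6, so 60 per arm.
- With 15% loss: 60/0.85 = 70.6, so 71.

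The stated 60 and 71 are reproduced. The plan does not give sidedness; a one-sided test would need 47. The whole 0.05 is spent on a single comparison at 90 minutes, so the sample size makes no allowance for the secondary tests.

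**2. Number of organism tests.** This assumes that each organism is tested at the three post-preparation times.

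- All entries: (6 + 5) × 3 = 33.
- Gardnerella and Bacteroides counted once: 9 × 3 = 27.
- By list: 6 × 3 = 18 (infection) and 5 × 3 = 15 (vaginosis).

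**3. Chance of at least one false positive.** Assumptions: equal products, normal test statistics with equal correlation r between the three times, independence between organisms, and a true 5% level for every test. The documents give no value for r; 0.6 and 0.8 are assumed.

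Let a be the chance that one organism gives p < 0.05 at one or more of the three times. By numerical integration a = 0.118 for r = 0.6 and 0.098 for r = 0.8 (independent times: 1 − 0.95³ = 0.143). Counting only results that favour chlorhexidine, the values are 0.059 and 0.049. For k organisms the chance is 1 − (1 − a)^k.

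| Set | k | Either direction, r = 0.6 | r = 0.8 | Favouring chlorhexidine, r = 0.6 | r = 0.8 |
|---|---|---|---|---|---|
| All entries | 11 | 75% | 68% | 49% | 43% |
| Distinct organisms | 9 | 68% | 61% | 42% | 36% |
| Infection list | 6 | 53% | 46% | 31% | 26% |
| Vaginosis list | 5 | 47% | 40% | 26% | 22% |

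Example: 1 − (1 − 0.118)^6 = 0.53.

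**4. Rare organisms.** Tests on sparse counts rarely reach their nominal level. A null simulation of the wider set of 34 to 40 secondary tests (60 per arm, Mann-Whitney tests for organism counts, within-patient correlation 0.3 to 0.9, 600 runs per setting) gave about 66 to 86% with organisms present in 3 to 30% of women. It gave about 45 to 59% with every organism at 2%. These prevalences are assumed. The figures in step 3 would fall in the same way.

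**The case against.** The strongest reply is that the trial has one clearly named primary outcome, is sized on it alone, and labels everything else secondary. Leaving secondary outcomes unadjusted is common in a small trial, and on this view only a sentence calling them exploratory is missing. The point about the primary stands in full: that test is not inflated, and nothing here weakens its result. The rest does not remove the concern, because the plan words the pathogen hypotheses as directional claims, gives them a significance rule, and nowhere calls them exploratory.

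The testing of each organism at each time is also an inference. The sentence on time points follows one about continuous variables, and the outcome is described as change over time. This is fair, and the figures are conditional on that reading. No other analysis of the organism counts is specified.

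A reader might go further and count about 40 secondary comparisons by adding contamination at 30 and 60 minutes (2), the 100,000 load (1), the Nugent score at three times (3) and infection (1) to the 33. That would give 1 − 0.95^40 = 87%. The documents do not support that as the size of the problem:

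- Load and infection belong to none of the three secondary hypotheses.
- The count takes the overlapping organisms twice; counting them once gives 34.
- The 87% needs independent tests, each with a true 5% error, although the same women are sampled repeatedly.
- It counts results in either direction, whereas the claim at risk is superiority of chlorhexidine.

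Infection does not strengthen the case either. At the 2.7% rate cited in the Background, about 71 × 0.027 = 1.9 cases per arm are expected. A significance test would then seldom be positive at all, which is a matter of power rather than of false positives.

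**Conclusion.** The concern holds for the two organism hypotheses. With equal products, and r assumed to be 0.6 to 0.8, the rule as written gives about a 61 to 75% chance of at least one nominally significant organism result, or 36 to 49% for one favouring chlorhexidine. Taken separately, the infection list gives about 46 to 53% and the vaginosis list about 40 to 47% in either direction. For a finding favouring chlorhexidine, the figures are 26 to 31% and 22 to 26%, against a nominal 2.5% for one test in that direction.

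These figures rest on the inferred organism-by-time testing, the assumed correlations, independence between organisms and full-level tests; rare organisms would lower them. That a false claim in favour of chlorhexidine is more likely than not cannot be established for the organism tests. The primary comparison and the 60 evaluable (71 enrolled) per arm stand as they are.

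**What to change.** In the Statistical Analysis section, before treatment assignments are joined to the data, state that:

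- Only contamination at 90 minutes carries a confirmatory claim, at two-sided 0.05.
- For each of the two organism hypotheses, there is one comparison per organism at 90 minutes, the primary time point, with the test named in advance. Holm adjustment is applied within each list as it now stands in Secondary Outcomes. The smallest p-value is then compared with 0.05/6 = 0.0083 (infection list) or 0.05/5 = 0.010 (vaginosis list).
- All other secondary results (contamination at 30 and 60 minutes, 100,000 load, Nugent scores, organism counts at other times, infections) are exploratory, reported as estimates with 95% intervals and without significance claims.

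This keeps both lists intact and limits the false positive chance to 5% per list, hence at most 10% over the two. Another time or summary measure per organism would also do if it is fixed in advance.

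The cost is analysis wording only, with no extra patients, samples or laboratory work. The downside is that fewer secondary results can be called significant, and the hypothesis on the 30 to 90 minute window would be described rather than tested at 30 and 60 minutes.
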